2.1.5.1 Additional Risks

PB2452 lacks an endogenous target, and in a human tissue panel cross-reactivity study utilizing PB2452-FITC, no staining was observed in any of the human tissues on the panel. Therefore, due to high binding specificity, the risk of off-target effects is considered low.

The 14-day extended single-dose non-clinical GLP toxicology study conducted in rats with PB2452 doses up to 2000 mg/kg did not identify a clinically relevant safety concern. The maximum human dose proposed for Phase 1 was approximately 250 mg/kg.

Potential risks based on class effects

• Infusion site reactions:

Possible risks associated with IV administration are redness, swelling, pain, induration, and sometimes infection at the administration site

• Anaphylactic-type and infusion reactions:

Although anaphylactic-type reactions are considered of importance due to their serious nature, they are rare. Acute anaphylactic reactions may include cardio-respiratory distress, chest pain, hypotension, dyspnea, bronchospasm, respiratory failure, urticaria, pruritus, angioedema, nausea, vomiting, diarrhea, hypotonia, and collapse

• Immunogenicity:

Development of antibodies to PB2452 might pose issues with a subsequent dose of PB2452, either an amnestic immunological reaction or, in the case of neutralizing antibodies, reduced efficacy. However, it is considered very unlikely that readministration will be required

• Thrombosis:

There is a risk of thrombosis following reversal of ticagrelor's therapeutic antiplatelet effect in patients with clinical conditions at very high risk of thrombosis, such as recent ACS or recent placement of a coronary stent

• Bleeding (aspirin and/or ticagrelor only):

Volunteers receiving pre-treatment with both aspirin and ticagrelor have a risk of bleeding during the clinical study

2.1.5.2 Benefits

Other than frequent assessments of overall health occurring during the screening, treatment, and follow-up periods of this study, there are no expected benefits from participation in this study.

2.2 Study Rationale

Current recommendations for management of bleeding in patients treated with antiplatelet therapies are suboptimal; they are mostly supportive and non-specific. Platelet transfusion, while useful for some antiplatelet agents, exposes patients to the known risks of blood products. Further, the efficacy of transfused platelets may be limited by exposure to circulating antiplatelet drug or metabolites if present. Moreover, it has been demonstrated that platelet transfusions do not reverse the effects of ticagrelor (Dalen M, 2013; Godier A, 2015; Maillard J, 2015; Teng, 2016).

An agent to rapidly reverse the anti-platelet effects of ticagrelor, and its active metabolite TAM, would fulfill an important unmet clinical need for those ticagrelor-treated patients:

- who have major or life-threatening bleeding
- who require urgent surgery or intervention associated with a high risk of bleeding

3 OBJECTIVES AND ENDPOINTS

The primary hypothesis for this trial is to evaluate whether intravenous PB2452 will result in reversal of the antiplatelet effects of ticagrelor.

3.1 Primary Objective and Endpoint

Primary Objective:

To demonstrate reversal of the antiplatelet effects of ticagrelor with intravenous PB2452 vs. placebo.

Primary Endpoint:

The primary study endpoint is the minimum % inhibition of platelet reactivity unit (PRU) assessed by VerifyNowTM PRUTestTM (VerifyNowTM, 2016) within 4 hours after the initiation of study drug. Percent inhibition of PRU is calculated as $100 * [(PRU_{bsl} - PRU_{trt})/PRU_{bsl}]$ where PRU_{bsl} refers to the PRU value measured before treatment with ticagrelor and PRU_{trt} refers to the PRU value measured before treatment with ticagrelor and PRU_{trt} refers to the PRU value measured posttreatment with the study drug.

Primary Endpoint Justification:

VerifyNowTM PRUTestTM is an effective and widely used clinical assay for assessment of ticagrelor's suppression of platelet function. It is a point-of-care assay that quantitatively assesses P2Y₁₂ dependent platelet aggregation. Degree of aggregation is reported on a PRU scale of 0-350. The lower limit of normal (LLN) platelet function is 180 PRU based on the assay's labeling.

Primary Endpoint Analysis:

Please refer to Section 9 of this protocol for further details.

3.2 Secondary Objectives and Endpoints

3.2.1 Secondary Objectives:

- 1. To evaluate the safety, tolerability, and immunogenicity of PB2452 in subjects treated with ticagrelor
- 2. To evaluate the pharmacokinetic (PK) profile of intravenous PB2452, ticagrelor, and its active metabolite (TAM) in blood and urine
- 3. To evaluate additional parameters of PB2452-mediated ticagrelor reversal by assessment of PRU using the VerifyNowTM PRUTestTM (VerifyNowTM, 2016) P2Y₁₂ assay and assessment of the platelet reactivity index (PRI) using the Vasodilator-stimulated phosphoprotein (VASP) assay

3.2.2 Secondary Endpoints:

1. Safety, tolerability and immunogenicity will be assessed by monitoring and recording of adverse events (AEs), including infusion site and systemic infusion reactions, clinical laboratory test results (hematology, coagulation, serum chemistry, and urinalysis), vital sign measurements (systolic and diastolic blood pressures, body temperature, respiratory rate, and heart rate), 12-lead electrocardiogram (ECG) results, physical examination findings, and immunogenicity

2. Plasma concentrations of total PB2452, unbound PB2452, total ticagrelor, total TAM, unbound ticagrelor, and unbound TAM, will be assessed at predetermined timepoints

PK parameters for PB2452 include:

- Observed maximum plasma concentration (C_{max})
- Area under the plasma concentration versus time curve (AUC) from time zero to the time of the last quantifiable concentration (AUC_{0-t})
- Time to reach the observed maximum plasma concentration (T_{max})
- AUC from time zero to 24 hours post-dose (AUC₀₋₂₄)
- AUC from time zero to 48 hours post-dose (AUC₀₋₄₈)
- Area under the plasma concentration versus time curve (AUC) from time zero to the time of the end of the dosing period (AUC_{0-tau})
- AUC from time zero extrapolated to infinity (AUC_{0-∞}; if data permit)
- Terminal elimination half-life ($t_{\frac{1}{2}}$; if data permit)
- Clearance (CL; if data permit)
- Volume of distribution (Vd)

PK parameters for ticagrelor/TAM include:

- C_{max}
- AUC_{0-last}
- T_{max}
- AUC₀₋₂₄
- AUC₀₋₄₈
- AUC_{0-tau}
- AUC_{0-∞}; if data permit
- t_{1/2}; if data permit

Urine PK endpoints:

Pooled urine samples to assess urine PB2452, ticagrelor, and TAM concentrations will be collected according to predefined intervals.

PK parameters for PB2452, ticagrelor, and TAM concentrations in urine for all subjects in the PK population to be calculated are:

- Total amount of drug excreted in urine at 24 hours (Ae₂₄) and at 48 hours (Ae₄₈)
- ae from time t1 to t2 hours including 0 to 6, 6 to 12, 12 to 24 and 24 to 48 hours (Aet1-t2)
- Fraction excreted in urine from 1 to 24 hours (Fe₂₄) and from 1 to 48 hours (Fe₄₈)
- Renal clearance (CLr) for 24 hours

- 3. Additional reversal endpoints:
 - Minimum %inhibition of PRI assessed by VASP within 4 hours after the initiation of study drug. %inhibition of PRI is calculated as 100 * [(PRI_{bsl} – PRI_{trt})/PRI_{bsl}]. PRI_{bsl} refers to the PRI value measured before treatment with ticagrelor and PRI_{trt} refers to the PRI value measured posttreatment with the study drug
 - PRU AUC for the first 4 hours
 - Proportion of subjects with normalized platelet reactivity units within 4 hours after the initiation of study drug Normalized platelet reactivity is defined as $PRU \ge 180$.
 - Proportion of subjects with ≥60%, ≥80%, and 100% of PRU response rate within 4 hours after the initiation of study drug. A PRU response is defined as the 100 *(PRU_{trt}/PRU_{bsl})
 - Time to 60%, 80%, 100% of PRU response rate within 4 hours after the initiation of study drug
 - Duration of 80% and 100% response rate by PRU
 - PRI AUC for the first 4 hours
 - Proportion of subjects with ≥60%, ≥80%, and 100% of PRI response rate within 4 hours after the initiation of study drug. A PRI response is defined as the 100 * (PRI_{trt}/PRI_{bsl})
 - Time to 60%, 80%, 100% PRI response rate within 4 hours after the initiation of study drug
 - Duration of 80% and 100% response rate by PRI
 - Percent reversal of PRU within 4 hours after the initiation of study drug. Percent reversal is calculated as 100 *[(PRU_{trt} PRU_{pre-trt})/(PRU_{bsl} PRU_{pre-reversal})]. PRU_{pre-trt} is defined as the PRU value prior to administration of study drug
 - Percent reversal of PRI within 4 hours after the initiation of study drug. Percent reversal is calculated as 100 * [(PRI_{trt} PRI_{pre-trt})/(PRI_{bsl} PRI_{pre-trt})]. PRI_{pre-reversal} is defined as the PRU value prior to administration of study drug

3.3 Other Prespecified Objectives Endpoints

3.3.1 Other Prespecified Objectives:

• Assessment of platelet function related biomarkers

3.3.2 Other Prespecified Endpoints

- Circulating levels of P-selectin and other platelet function-related biomarkers at baseline and post-initiation of PB2452
- Proportion of subjects with known single-nucleotide polymorphisms related to $P2Y_{12}$ receptor function

4 STUDY PLAN

4.1 Study Design

This phase 2B study is a multi-center, randomized, double-blind, multicenter, placebo-controlled study. The study is designed to evaluate the efficacy of PB2452 in reversing the anti-platelet effects of ticagrelor as part of a dual antiplatelet regimen and to evaluate the safety and tolerability of PB2452 in subjects aged 50-80 years old.

Approximately 200 subjects between 50-80 years old will be enrolled in the US and other countries at the discretion of the Sponsor across 5-15 sites. The subjects will be randomized at a ratio of 3:1 receiving either the PB2452 investigational study drug or placebo. Hence, a total of approximately 150 subjects will be receiving PB2452 and approximately 50 subjects will be receiving placebo.

All subjects will be administered enteric coated aspirin 81 mg daily for at least 7 days prior to initiation of study drug for a total of 8 doses. Ticagrelor tablets will be administered prior to initiation of study drug with a 180 mg oral loading dose, followed by 90 mg bid for a total of 5 doses of ticagrelor. Two hours following the last dose of ticagrelor on morning of Day 1, subjects will receive either PB2452 or a placebo administered intravenously (IV) to assess reversal at peak ticagrelor plasma concentrations.

The infusion regimen is as follows:

- An initial intravenous (IV) bolus infusion consisting of a 6 g of study drug infused over 10 minutes followed immediately by an additional 6 g loading regimen of PB2452 infused over 4 hours
- A maintenance regimen of 6 g infused over 12 hours will immediately follow completion of the loading regimen for a total infusion time of approximately 16 hours

If a subject is taking a moderate or strong CYP3A inhibitor, a 36 g alternative regimen of PB2452 will be administered intravenously starting at 2 hours after the final dose of ticagrelor:

- An initial 12 g bolus of PB2452 infused over 10 minutes followed immediately by an additional 12 g loading infusion of PB2452 over 6 hours
- A 12 g maintenance infusion of PB2452 administered over 18 hours will immediately follow completion of the loading regimen for a total infusion time of 24 hours and 10 minutes

No interim analysis or subsequent long-term extensions are planned.

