2. INTRODUCTION

The purpose of this plan is to prospectively outline in detail the data derivations, statistical methods and presentations of data so that valid conclusions can be reached to address the study objectives outlined in the PB2452-PT-CL-0003 protocol, dated 12 August 2019.

This Statistical Analysis Plan (SAP) will be signed before database lock and data analyses. The planned analyses identified in this SAP may be included in regulatory submissions and/or future manuscripts. Exploratory analyses, not identified in this SAP, may be performed to support the clinical development program. Any data analyses performed after signing of this SP and database lock will be considered post-hoc analyses, except if required by a regulatory agency. Any post-hoc or unplanned analyses that are performed but not identified in this SAP will be clearly identified in the clinical study report (CSR).

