- Total amount of drug excreted in urine at 24 hours (Ae_{24}) and at 48 hours (Ae_{48})
- AE from time t_1 to t_2 hours including 0 to 6, 6 to 12, 12 to 24 and 24 to 48 hours (Ae_{t1-t2})
- Fraction excreted in urine from 1 to 24 hours (Fe_{24}) and from 1 to 48 hours (Fe_{48})
- Renal clearance (CLr) for 24 hours.

Additional Reversal Endpoints

- Minimum %inhibition of PRI assessed by VASP within 4 hours after the initiation of study drug. %inhibition of PRI is calculated as $100 * [(PRI_{bsl} - PRI_{trt})/PRI_{bsl}]$. PRI_{bsl} refers to the PRI value measured before treatment with ticagrelor and PRI_{trt} refers to the PRI value measured posttreatment with the study drug.
- PRU AUC for the first 4 hours.
- Proportion of patients with normalized platelet reactivity units at any time within 4 hours after the initiation of study drug. Normalized platelet reactivity is defined as $PRU \geq 180$.
- Proportion of patients with $\geq 60\%$, $\geq 80\%$, and 100% of PRU response rate at any time within 4 hours after the initiation of study drug. A PRU response is defined as the $100 * (PRU_{trt}/PRU_{bsl})$.
- Time to 60% , 80% , 100% of PRU response rate within 4 hours after the initiation of study drug.
- Duration of 80% and 100% response rate by PRU.
- PRI AUC for the first 4 hours.
- Proportion of patients with $\geq 60\%$, $\geq 80\%$, and 100% of PRI response rate within 4 hours after the initiation of study drug. A PRI response is defined as the $100 * (PRI_{trt}/PRI_{bsl})$.
- Time to 60% , 80% , 100% PRI response rate within 4 hours after the initiation of study drug
- Duration of 80% and 100% response rate by PRI
- Maximum percent reversal of PRU within 4 hours after the initiation of study drug. Percent reversal is calculated as $100 * [(PRU_{trt} - PRU_{pre-trt})/ (PRU_{bsl} - PRU_{pre-trt})]$. $PRU_{pre-trt}$ is defined as the PRU value prior to administration of study drug.
- Maximum percent reversal of PRI within 4 hours after the initiation of study drug. Percent reversal is calculated as $100 * [(PRI_{trt} - PRI_{pre-trt})/ (PRI_{bsl} - PRI_{pre-trt})]$. $PRI_{pre-trt}$ is defined as the PRI value prior to administration of study drug.

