4.1. Study Treatments and Dose Administration

This Phase 2B study is a randomized, double-blind, multicenter, placebo-controlled study conducted across United States. The study is designed to evaluate the efficacy of PB2452 in reversing the anti-platelet effects of ticagrelor and to evaluate the safety and tolerability of PB2452 in subjects aged 50-80 years old.

Approximately 200 subjects 50-80 years old inclusive will be enrolled across US or if needed other countries at 5-15 sites. The subjects will be randomized at a ratio of 3:1 receiving either the PB2452 investigational study drug or placebo. Hence, a total of approximately 150 subjects will be receiving PB2452 and approximately 50 subjects will be receiving placebo.

All subjects will be administered aspirin 81 mg daily for at least 7 days prior to initiation of ticagrelor pretreatment with a 180 mg oral loading dose of ticagrelor, followed by 90 mg bid for a total of 5 doses of ticagrelor. Two hours following the last dose of ticagrelor, subjects will be randomized to either PB2452 (investigational / study drug) or a matching placebo administered intravenously (IV) to assess reversal at peak ticagrelor plasma concentrations.

The infusion regimen is as follows:

- An initial IV bolus infusion consisting of a 6 g of study drug infused over 10 minutes followed immediately by an additional 6 g loading regimen of PB2452 infused over 4 hours,
- A maintenance regimen of 6 g infused over 12 hours will follow completion of the loading regimen for a total infusion time of approximately 16 hours.

No interim analysis or subsequent long-term extensions are planned.

Table 1 Schedule of Events

Procedure	Out patient		Out patient			Treatment (in house)			Out patient	Out patient
	Screening ^a		Check-in/ Pretreatment			Rand		Subject DC	FUP	FUP EOS
Study Day(s)	-45 to -4	-7	-3	-2	-1	1	2	3	7	35±3
Sign informed consent	X									
Inclusion/exclusion criteria	X		X		X					
Demographics	X									
Medical history	X									
Urine drug screen	X		X							
Urine alcohol screen	X		X							
Serum pregnancy test ^b	X		X							X
Serology testing	X									
Stool for occult blood	X									
Admission to study clinic			X							
Physical examination ^{c,d}	X ^c		X ^c						X ^d	X ^d
Vital sign measurements ^e	X		X			X	X	X	X	X
12-lead ECG ^f	X			X	X	X			X	X
Clinical laboratory testing	X		X		X		X		X	X
Randomization						X				
Drug administration										
ASA 81 mg QD ^g	X	X	X	X	X	X				
Ticagrelor administration ^h				X	X	X				

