- g ASA 81 mg will be taken on Days -7, -6, -5, -4, -3, -2, -1, and on Day 1 (2 hours before study drug is started). Subjects who enter the study already taking ASA daily must document a daily ASA 81 mg dose between Day -7 and Day -3. Patients will receive daily ASA 81 mg between Day -3 (or Day -2 if the patient took ASA 81mg on Day -3 prior to Check-in) and Day 1 at the clinical facility and will suspend further ASA dosing until discharge from the clinical facility.
- h Beginning in the morning on Day -2, a single dose of oral ticagrelor 180 mg will be given, followed by oral ticagrelor 90 mg every 12 hours for 4 additional doses through to Day 1 (2 hours before study drug is initiated; this will be 5 total doses of ticagrelor).
- i PB2452/placebo will be administered at Hour 0 of Day 1.
- j Blood samples for determination of plasma PB2452, plasma ticagrelor/TAM and unbound plasma ticagrelor/TAM will be collected within 10 minutes prior to the initiation of PB2452/placebo infusion (Hour 0) and at 5, 10, 30 minutes and 1, 2, 4, 8, 12, 20, 24, 36, and 48 hours after initiation of study drug infusion. And on days -2, 1, 2, 3, 7, and 35 ± 3 after initiation of study drug infusion.
- k Blood samples for PD analysis (PRU/VASP testing) will be collected at the following timepoints: Day -2 (up to 60 minutes prior to first ticagrelor dose) and Hour 0 (up to 10 minutes prior to PB2452/placebo infusion), 5, 10, 30 minutes, 1, 2, 4, 8, 12, 20, 24, 36 and 48 hours after initiation of PB2452/placebo infusion.
- If there is sufficient material leftover from PK and/or PD blood samples, additional platelet function-related biomarkers, such as P-selectin, will be tested to support hypothesis generation for future studies.
- l Subjects may be required to return to the site for collection of additional follow-up samples, if the sample collected at Day 35 ± 3 tests positive for treatment-emergent ADAs. These visits may occur approximately 3 months after the final study visit and approximately every 6 months thereafter or until antibody levels return to baseline level.
- m Infusion site assessments will be performed for all subjects within 15 minutes before initiation of PB2452/placebo infusion at Hour 0, 1, 3, 24, and 48 hours after initiation of PB2452/placebo infusion, and on Day 7.

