10. SAFETY

Safety will be assessed by examination of adverse events, physical examination findings, vital signs, clinical laboratory measurements, antibodies to study drug and 12 lead ECGs. These results will be presented for the Safety Population by treatment group and overall.

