11. PHARMACOKINETIC ANALYSIS

The ticagrelor and TAM pharmacokinetic results will be analyzed for all randomized subjects, and the PB2452 results will be analyzed for the PK Population.

Plasma Concentrations

Plasma concentrations will be listed by nominal timepoints and subject, and summarized descriptively (number of subjects, mean, SD, coefficient of variation [CV], geometric mean, geometric CV, median, minimum, and maximum). Plasma concentration versus time profiles for each subject will be presented graphically. The mean plasma concentration versus time profiles will be presented graphically both on the linear and semi-log scale. All concentration plots will be presented using nominal times from the time of PB2452 dosing.

Plasma concentration values below the limit of quantification (BLQ) will be set to zero for calculation of all summary statistics except for geometric mean and geometric CV. In case any value is BLQ, the geometric mean and geometric CV will be presented as NA. For the semi-log plots if the mean value is zero (i.e., if all values are BLQ at a timepoint) then it will be set to LLOQ/2 in the plot.

Scatter plots of pharmacokinetic data versus total and unbound PB2452 plasma concentrations may be prepared for including both treatment groups with placebo group concentration set to zero.

Plasma Pharmacokinetic Parameters

Plasma pharmacokinetic parameters of PB2452, ticagrelor, and TAM will be determined using noncompartmental models using Phoenix WinNonlin Version 8.1 or higher and summarized by time point using descriptive statistics (number of subjects, mean, SD, CV, median, minimum, and maximum). In addition, geometric means and geometric CVs will be reported for AUCs and Cmax. Actual sampling times, rather than scheduled sampling times, will be used in all calculations of PK parameters.

For calculating the PK parameters, BLQ values will be treated as zero with the exception that a BLQ value between 2 quantifiable concentrations will be set as missing. If 2 or more consecutive BLQ concentrations are followed by quantifiable concentrations in the terminal phase, those concentrations after BLQ concentrations will be treated as missing. Missing concentrations will not be imputed for calculating the PK parameter.

The terminal elimination phase will be identified by regression analysis using logarithmically transformed plasma concentrations. An elimination phase will be considered invalid for the following situations:

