- It has less than 3 data points;
- It has a positive slope (or correlation coefficient $[r]>0$);
- Adjusted $r^2 \leq 0.8$. (Adjusted $r^2 = 1 - \{(1-r^2) \times (n-1)\} / (n-2)$, where n is the number of data points in the regression and r^2 is the square of the correlation coefficient.).
- In cases where $C_t/\lambda z$ (i.e., the extrapolated portion of $AUC_{0-\infty}$) is $\geq 20\%$ of $AUC_{0-\infty}$, $AUC_{0-\infty}$ will be considered invalid.

Urine PK Concentration

Pooled urine samples to assess urine PB2452, ticagrelor and TAM concentrations will be collected over the following intervals: before dosing (within 60 minutes prior to the first ticagrelor dose on Day -2) and 0 to 6, 6 to 12, and 12 to 24 hours post dose.

For PB2452 concentration, urine concentration will be summarized by the time-intervals mentioned above. For Ticagrelor and TAM concentrations, the summary will be presented by treatment.

For each analyte, urine concentration and volume data will be listed by collection interval for each subject.

Urine Parameters

The urine PK parameters Ae_{24} , Ae_{48} , and Ae_{t1-t2} (for 0 to 6, 6 to 12, 12 to 24 and 24 to 48 hours), Fe_{48} , and CL_r for PB2452, ticagrelor and TAM in urine will be listed by subject and summarized for using descriptive statistics (number of subjects, mean, SD, CV, median, minimum, and maximum).

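### The SAP describes only the 18 g regimen, so its PK, late PRU/PRI and safety summaries would pool it with the 36 g regimen in protocol Version 2

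*Protocol*

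**What the plan says.** **Protocol Version 2 (28 May 2021).** The standard regimen is 6 g over 10 minutes, 6 g over 4 hours, then 6 g over 12 hours. Section 4.1 continues: "If a subject is taking a moderate or strong CYP3A inhibitor, a 36 g alternative regimen of PB2452 will be administered intravenously". That regimen is 12 g over 10 minutes, 12 g over 6 hours and 12 g over 18 hours, 24 h 10 min in all. Placebo infusions mirror the active ones. Section 2.1.2.2 says the study is to confirm the reversal, safety, tolerability and immunogenicity profile of 18 g over 16 hours.

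**SAP.** Section 2 ties the plan to the "study objectives outlined in the PB2452-PT-CL-0003 protocol, dated 12 August 2019". Section 4.1 gives only three 6 g steps, the last of which "will follow completion of the loading regimen for a total infusion time of approximately 16 hours". The SAP contains no 36 g regimen and no reference to CYP3A inhibitors. Its outputs are defined as follows.
- PK (section 11): ticagrelor and TAM are analysed for all randomised subjects, and "the PB2452 results will be analyzed for the PK Population".
- Safety (section 10): "These results will be presented for the Safety Population by treatment group and overall".
- PRU/PRI (sections 9.1 and 9.2): percent inhibition of PRU at all time points, and PRU and PRI responder proportions by time point and treatment.
- Subgroups (section 6.2): optional summaries by age group and for other subjects of interest. Renal impairment is the example given; regimen is not named.

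**The concern.** One column headed PB2452 would hold two total doses, two bolus sizes and two infusion lengths. A pooled Cmax or AUC describes neither regimen. The 20 and 24 hour PRU/PRI results matter most for the claim of sustained reversal, and they would combine subjects whose infusion has ended with subjects still receiving drug.

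Ticagrelor/TAM PK is affected in both arms. Inhibitor users are expected to have higher ticagrelor levels, which is why the protocol doubles their PB2452 dose.

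On safety, the Phase 2A 36 g cohort described in protocol section 2.1.2.2 was aged 18 to 50. This trial would give 36 g to subjects aged 50 to 80, and no planned table would show their results separately.

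**Working it through.** **1. The plan's own figure.** SAP section 4.2 claims more than 99% power with 150 v 50 subjects, difference 15, SD 20 and two-sided alpha 0.05. The standard error is 20 × √(1/50 + 1/150) = 3.266, and 15/3.266 = 4.593. Power is Φ(4.593 − 1.960) = 99.6% (99.5% with the noncentral t). The claim reproduces.

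**2. Drug infused by time.** Inputs are the step doses and durations in protocol section 4.1. For the 36 g regimen at 20 h: 12 + 12 + 12 × (20 − 6.17)/18 = 33.2 g.

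| Time from start | 18 g regimen | 36 g regimen | Ratio |
|---|---|---|---|
| 10 min | 6 g | 12 g | 2.00 |
| 4 h | 11.75 g | 19.67 g | 1.67 |
| 20 h | 18 g | 33.22 g | 1.85 |
| 24 h | 18 g | 35.89 g | 1.99 |
| After 24 h 10 min | 18 g | 36 g | 2.00 |

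At the 20 h and 24 h samples, 18 g subjects have been off infusion for 3 h 50 min and 7 h 50 min. Subjects on 36 g are still being infused at both.

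**3. Effect on pooled exposure.** Protocol section 2.1.4.1 reports Cmax and AUC as roughly dose-proportional. I assume this extends to 36 g. Let f be the share of PB2452 subjects on 36 g, set the 18 g mean to 1 and the 36 g mean to 2, and let c be the CV within each regimen.

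- Pooled mean = 1 + f
- Pooled variance = (1 − f)c² + f(2c)² + f(1 − f)

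For f = 0.05 and c = 0.20: variance = 0.038 + 0.008 + 0.0475 = 0.0935, SD = 0.306, mean = 1.05, CV = 29.1%.

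| Assumed share (of 150) | Rise in mean | CV if c = 4.8% | CV if c = 20% | CV if c = 28.9% |
|---|---|---|---|---|
| 2% (3) | 2% | 14.6% | 24.4% | 32.2% |
| 5% (about 8) | 5% | 21.3% | 29.1% | 36.1% |
| 10% (15) | 10% | 27.7% | 34.3% | 40.5% |

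The outer values of c are the range in section 2.1.4.1 for Phase 1 Cohorts 1-3 (0.1 to 1 g, 30-minute infusions, no ticagrelor), so they are only a guide. The 20% is an assumed middle value. The factor of 2 suits measures that follow bolus size or total dose. For AUC0-24 it is somewhat high, because the infused-dose ratio is below 2 for most of that period.

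**4. Which subjects supply the terminal-phase parameters.** SAP Table 1 takes PK samples at times including "4, 8, 12, 20, 24, 36, and 48 hours after initiation of study drug infusion". After the end of infusion and up to 48 h, this leaves four samples for 18 g (20, 24, 36, 48 h) and two for 36 g (36, 48 h). SAP section 11 rejects an elimination phase if "It has less than 3 data points". A 36 g subject therefore needs a quantifiable Day 7 sample, about 96 h after the 48 h one. At the longest half-life in section 2.1.4.1 (9.2 h, from the low-dose cohorts), 96/9.2 = 10.4 half-lives, which leaves 0.07% of the 48 h level. The assay limit is not given. Half-life, CL and AUC0-∞ would probably come from 18 g subjects only, while Cmax and the partial AUCs come from everyone.

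**5. Primary comparison.** If inhibitor users were removed from both arms in equal share, power by the method in step 1 would be 99.5%, 99.4% or 99.2% at 2%, 5% or 10%, and still 97.0% at 30%.

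**The case against.** The strongest reply is that this is housekeeping. The share on 36 g is not stated and could be close to zero: subjects are in good general health on stable medication, and new medication is barred from Day -30 to Day 3. Dose received is recorded, individual PK profiles are plotted, adverse events are listed, and SAP section 6.2 would allow a separate summary. Reporting safety by arm matches the randomised comparison, and a small 36 g column says little: with no events in 3, 8 or 15 subjects, the exact 95% upper limit, 1 − 0.025^(1/n), is 71%, 37% or 22%.

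Much of this stands. It limits the gap to the planned summary tables and leaves its size unknown. It does not remove the gap. The option in section 6.2 neither requires a split nor names regimen, and a reader of the tables would not know that two regimens had been combined. Users of inhibitors are also plausible: hypertension on up to two drugs is allowed, and section 2.1.2.2 names diltiazem and verapamil as moderate inhibitors.

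A reader might infer more than the documents support:
- **That the SAP specifies a pooled duration-of-reversal analysis.** It lists "Duration of 80% and 100% response rate by PRU" as an endpoint, but sections 9.2 and 9.3 give no analysis of it. Pooling there is only what by-arm reporting would imply.
- **That half-life, CL and AUC0-∞ are distorted.** Both documents make these PB2452 parameters conditional on the data, and step 4 suggests they would mostly describe 18 g.
- **That the end-of-infusion ECG is mistimed for 36 g.** The 16 h 10 min clock time is a parenthesis in protocol section 6.1. Footnote h of the schedule gives no clock time, and its ECG at 24 h ± 30 min spans the end of the 36 g infusion.
- **That strong-inhibitor users are wrongly included or under-dosed.** The stated rationale does name only moderate inhibitors. But exclusion 5 refers to the ticagrelor label, which is not supplied, so the documents do not settle who is eligible.
- **That the benefit-risk case for 36 g is deficient.** Section 2.1.2.2 describes the Phase 2A 36 g cohort, and clinical detail is left to the Investigator's Brochure, also not supplied.

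**Conclusion.** The point holds as a mismatch between the SAP and the current protocol. The SAP would pool 18 g and 36 g subjects in PB2452 concentrations by time, Cmax, AUC0-24, AUC0-48, AUC0-last and amounts excreted in urine. It would do the same in ticagrelor/TAM PK, in PRU/PRI at 20 and 24 h, and in the safety tables. These would not isolate the 18 g profile.

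The figures of 2% to 10% on the mean, and a CV of 24% to 34% in place of 20%, rest on an assumed share of 2% to 10% and on dose proportionality up to 36 g. With few or no subjects on 36 g, the effect is correspondingly small or absent.

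It would be wrong to infer that the primary result is in doubt. Inhibitor use is fixed before randomisation, placebo subjects who use inhibitors are in the comparison, and power is barely touched. The 2019 protocol is not supplied, so the documents do not show when the 36 g regimen was added. That does not change the conclusion, because the SAP omits it either way.

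**What to change.** Before database lock:
1. Update the SAP to protocol Version 2 and describe the 36 g regimen and its trigger in SAP section 4.1.
2. Present PB2452 PK and ticagrelor/TAM PK by regimen (18 g, 36 g) as well as pooled. For ticagrelor/TAM, split placebo by inhibitor use in the same way.
3. Present PRU and PRI by time point, and any duration-of-reversal summary, by regimen as well as pooled.
4. Add a descriptive TEAE summary by regimen.
5. State in SAP section 11 how many subjects on each regimen contribute to half-life, CL and AUC0-∞.

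As an optional tidy-up, delete the 16 h 10 min parenthesis from the Day 1 ECG line in protocol section 6.1.

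The cost is a SAP revision and a few table columns, with no added subjects, visits or samples and no change to the primary test. The 36 g columns will be imprecise. Because inhibitor use sets the regimen, they should be labelled descriptive and not read as a dose comparison.
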